The issue of non-adherence for drugs with continuous use in SLE is a difficult problem to measure and can reach 76% of cases, bringing serious consequences for the patient related to changes in prescriptions (Costedoat-Chalumeau et al., 2013). In this context, it is relevant that some studies have shown that plasma dosage of hydroxychloroquine is a reliable parameter for adherence because the drug has a long half-life and can be detected in blood tests.

In adult SLE, it has been reported that HCQ blood concentrations below 1000 ng/mL are associated with disease activity, it is a strong predictor of exacerbation in the following six months (Costedoat-Chalumeau et al., 2006). It is emphasized, however, that the concentrations of HCQ in the total blood varied greatly among the patients in this study, despite the prescription of the same daily dose. In this study, however, the evaluation of lupus activity was global and did not focus on renal involvement, and it was only mentioned that 10 patients had active nephritis. Other studies are therefore necessary to define blood levels of HCQ that will be predictors of outbreaks of renal activity, whose involvement is present in more than 50% of patients and which is the greatest therapeutic challenge of the disease. In this context, it is interesting that the use of this drug is associated with higher renal survival (Fessler et al., 2005) together with a better response to standard treatment with mycophenolate mofetil in patients with SLE (Kasitanon et al., 2006), reinforcing the importance of an adequate control of its use in this condition. It is also relevant in the context of treatment that antimalarials have a long half-life of approximately 40 days and there is a delay to reach plasma concentration with a therapeutic effect expected only after 3 months or more of treatment (Rodriguez-Caruncho et al., 2014). Monitoring the level of this medication, which was established as at least 1000 ng/mL, would certainly be very useful in determining whether a higher attack dose would allow this therapeutic effect to be achieved more quickly. In addition, monitoring HCQ levels would allow assessing whether a reduction in the weekly HCQ dose

after a prolonged period of treatment with tissue depot of the drug would be possible to avoid the most feared side effect that is retinopathy with loss of vision. This side effect is associated with the cumulative dose of an (Wolfe et al., 2010; Jallouli et al., 2015).

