SUBPROJECT 1B

Prospective, randomized and controlled study comparing the frequency of SLE and jSLE activity of patients with a stable dose of HCQ and patients with dose reduction of this drug and its correlation with blood levels of its metabolites diseases.

SLE AND jSLE

Background

It takes at least 6 months of HCQ use to achieve its best efficacy (Clark et al., 1993). In SLE, regular use of HCQ promotes a decrease in inflammatory outbreaks of the disease (Ruiz-Irastorza et al., 2010) and its withdrawal is associated with worsening activity remission (Tsakonas et al., 1998 - The Canadian Hydroxychloroquine Study Group). Its action is due to a modulating effect on the immune response, influencing the presentation of antigens and production of pro-inflammatory cytokines, which are probably mediated mainly by inhibition of Toll-like receptors-7 and -9 (Wallace et al., 2012). Adequate serum levels of HCQ metabolites are related to a better efficacy in the treatment of the cutaneous form of lupus (Francès et al., 2012) and HCQ concentrations in the blood lower than 1,000 ng/mL determined by HPLC have been associated with higher inflammatory activity of SLE (Costedoat-Chalumeau et al., 2006). Monitoring of HCQ in the blood would allow assessing whether, after a prolonged period of treatment, which causes a tissue deposit of the drug in the skin, a reduction in the weekly dose would be possible. In addition, the measurement of HCQ in saliva could offer a good alternative for blood levels, because it is less invasive, as previously demonstrated with other drugs (Ruiter et al., 2012). The goal for reduced HCQ dose is to avoid retinopathy with vision loss, without risk of increased outbreaks of disease activity. Retinopathy is the most feared side effect of HCQ use and is associated with the cumulative dose of antimalarial (Wolfe et al., 2010). The new recommendation of the American Ophthalmology Association of 2011 determines that ophthalmological control of the use of antimalarials must necessarily include campimetry and at least one more objective examination such as multifocal electroretinogram, optical coherence tomography (SD-OCT) (Marmor et al., 2011). Our objective is to determine the mechanism of HCQ-induced injury through an evaluation of the correlation of functional and structural retinal damage, evaluated by central visual field examination (campimetry) and SD-OCT measurements, with segmentation of the outer layer of the retina (pigment epithelium). The proposed acquisition of a campimeter dedicated to the research intends to validate the isolated use of campimetry, limited to the 10-2 Humphrey field, as the gold standard of this evaluation.

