
In addition, it is extremely important to evaluate whether the reduction of the weekly dose of HCQ after a long period of use of this therapy would be able to maintain inhibition of TLR-7 and -9.

Objectives primary:

- Compare the frequency of outbreaks of disease activity (SLE and jSLE) in patients using standard dose (HCQ 400 mg/day) vs. patients with reduced dose (HCQ 400 mg/3X week) and its correlation with blood and saliva levels of the drug. Secondary: - Compare frequency of retinopathy in patients using standard dose (HCQ 400 mg/day) vs. patients with reduced dose (HCQ 400 mg/3X week) and its correlation with HCQ blood levels.

- Verify a possible longitudinal correlation of HCQ concentrations with the production of interferon-alpha and TNF by plasmacytoid dendritic cells.

- Correlate blood and salivary levels of HCQ and its metabolites in patients with SLE and JSLE with adherence to this treatment.

- Correlate functional and structural damage of the retina, evaluated by central visual field examination (campimetry) and SD-OCT measurements, with segmentation of the outer layer of the retina (pigment epithelium).

- Establishment of a pharmacokinetic-pharmacodynamic model of hydroxychloroquine dose reduction in patients with SLE.

NUMBER OF INDIVIDUALS

Total number of patients required for the study= 256 (SLE and JSLE).

STUDY DESIGN

Randomized controlled prospective study of non-inferiority of one year of follow-up of patients with SLE and JSLE in remission with HCQ use (stable dose of 400 mg/day for at least five years).

Patients will be randomized into two groups: no daily dose reduction group (HCQ 400 mg/day) and reduction group (HCQ 400 mg/day - 3X week). Patients will be evaluated for the activity of the underlying disease in a "blind" way. HCQ concentrations will be measured at the entrance, 6 months and 12 months after.

The groups will be compared for episodes of disease activity (clinical and laboratory parameters). The production of interferon-alpha and TNF by plasmacytoid dendritic cells will be evaluated in the same period in a subgroup of patients.

The following indexes will be used to assess disease activity:

- SLE and JSLE: SLEDAI-2K (Gladman et al., 2002) and active disease randomly defined as SLEDAI-2K \geq 6.

- Renal activity: BP, urine type I, protein and creatinine in an isolated urine sample, serum creatinine, C3, C4, anti-dsDNA, according to the recommendations of the ACR (Hahn et al., 2012).

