- LES and jSLE (ACR criteria) (Hochberg, 1997);
- use of HCQ at a dose of 400 mg/day for at least 3 years.

Exclusion criteria:

- alcoholism;
- renal dialysis;
- concomitant infectious process;
- acute and chronic liver diseases;
- concomitant use of some drugs that interact with HCQ (cimetidine, antacids, digoxin, aminoglycosides, penicillin, neostigmine, pyridostigmine).

RELEVANT METHODS - Ophthalmological assessment: central visual field examination (campimetry) and SD-OCT measurements, with segmentation of the outer layer of the retina (pigmentary epithelium).

- Blood levels of HCQ will be determined by HPLC MS/MS (Munster et al., 2002).

- Pharmacokinetic analysis: The pharmacokinetic parameters of hydroxychloroquine will be calculated in the 24 h dose range based on the total plasma concentration versus time curves. The Winnonlin program, version 4.0 (PharsightCorp., Mountain View, California, USA) and the Non-linear mixed effect level (NONMEM) program will be employed. The area under the plasma concentration curve versus time will be calculated in the 24-h dose interval by the trapezoid method on days 0 and 120. The apparent total clearance (CIT/F) will be obtained through the equation: $CIT/F = Dose/AUC_{0-24}$. The apparent distribution volume (Vd/F) will be calculated by the standard software equation. The hydroxychloroquine-free concentration will be determined by the dosage in saliva. The PK-PD analysis will be performed using as pharmacokinetic parameters the total and free plasma concentrations of hydroxychloroquine and, as a pharmacodynamic parameter, we will use the clinical/laboratory indices obtained by the evaluation of SLEDAI-2K (American College of Rheumatology). The PK-PD model will be developed using the non-linear mixed effect level (NONMEM).

- Others, the same as described in subproject 1A.

Safety

Monitoring of outbreaks of inflammatory activity (flare) and identification of retinopathy.

WITHDRAWALS

Signs of retinopathy.

ORIGINALITY WITH IMPACT on

Healthcare

To date, there is no study demonstrating that the reduction of HCQ dosage after tissue depot caused by a prolonged time of use of the drug can be safely performed in SLEJ and SLE, without increasing the number of outbreaks of inflammatory activity.

The expected care impact is a reduction of severe ophthalmologic event with the reduction of the HCQ dose and the expansion of the time of use of the drug that has a direct impact on the control of disease activity.

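### Subproject 1B examines eyes at entry and exit, but its retinopathy analysis states no use of the entry values or of prior hydroxychloroquine exposure

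*Combined protocol and SAP*

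**What the plan says.** The Background of Subproject 1B gives the purpose of the lower dose: "The goal for reduced HCQ dose is to avoid retinopathy with vision loss". It also names what drives the harm: "Retinopathy is the most feared side effect of HCQ use and is associated with the cumulative dose of antimalarial". The Introduction makes the same link.

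The retinopathy item among the secondary objectives begins "Compare frequency of retinopathy in patients using standard dose (HCQ 400 mg/day" and sets that group against "patients with reduced dose (HCQ 400 mg/3X week) and its correlation with HCQ blood levels". The other eye objective is "Correlate functional and structural damage of the retina, evaluated by central visual field examination (campimetry) and SD-OCT measurements". That one relates two kinds of eye finding to each other, not to exposure.

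Study Design schedules a full eye examination, with visual field and SD-OCT, at entry and at study end. It also lists age, weight, disease duration and time of HCQ use among the data to collect, but for comparing active with inactive disease. Retinopathy is not among the exclusion criteria, and signs of it are the only withdrawal reason given. The statistical analysis paragraph has a log-rank test for flare and, for other variables, Fisher or chi-square tests and t or Mann-Whitney tests. It names no covariate and no eye model.

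Minimum prior use is "stable dose of 400 mg/day for at least five years" in Study Design and "use of HCQ at a dose of 400 mg/day for at least 3 years" in the inclusion criteria. Both figures are used below.

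**The concern.** The eye analysis leaves out two things that 1B already collects.

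The first is the entry eye value. Comparing exit values alone leaves all pre-existing variation between patients in the error term. With no retinopathy exclusion, a frequency counted at exit mixes patients who arrived with retinopathy and patients who developed it. If signs of retinopathy lead to withdrawal, the cases that matter most may also be missing from an exit count.

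The second is prior exposure. The plan treats cumulative dose as the driver, but the two exposures it uses are arm and blood level. One year of randomised dosing moves cumulative dose little in patients with years of prior use, and a current level says little about those years. A null result on either would be weak evidence about cumulative-dose toxicity, and nothing in 1B warns the reader of that.

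**Working it through.** **1. The plan's own figure.** The only sample size in 1B is for flare: success 84% in both arms, margin 12%, power 80%, alpha 5%, losses 10%. Taking alpha as one-sided, n = 2 × 0.84 × 0.16 × (1.645 + 0.842)² / 0.12² = 115.4, so 116 per arm. Multiplying by 1.1 gives the stated 128 (dividing by 0.9 gives 129). Nothing is calculated for retinopathy. After 10% losses, 128 × 0.9 ≈ 115 per arm remain.

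**2. What the arms change.** Daily dosing gives 0.4 g × 365.25 = 146.1 g a year. Three days in seven gives 146.1 × 3/7 = 62.6 g. The difference is 83.5 g, or 4/7 (0.571) of a year of standard dosing. As a share of the standard-arm total at month 12:

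| Prior years at 400 mg/day | Standard-arm total (g) | Share |
|---|---|---|
| 3 | 584.4 | 14.3% |
| 5 | 876.6 | 9.5% |
| 10 (illustrative) | 1607.1 | 5.2% |

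**3. What the blood level reflects.** The Introduction gives a half-life of about 40 days, so a year is 365/40 ≈ 9 half-lives. On simple first-order decay (an assumption), a month-12 level reflects recent dosing, not the years before entry.

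**4. Size of a one-year arm effect.** The documents do not give the spread of prior use. If it is uniform over 3–10, 5–15 or 5–25 years (assumed), its SD is 2.02, 2.89 or 5.77 years, and the arm contrast is 0.571/SD = 0.28, 0.20 or 0.10 SD of prior exposure. If a continuous eye measure is linear in cumulative dose with correlation r of 0.1 to 0.3 (assumed), the expected arm difference is r times that ratio: 0.010–0.028 SD at r = 0.1 and 0.030–0.085 SD at r = 0.3.

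**5. Precision with and without the entry value.** Unadjusted 95% half-width: 1.96 × √(2/115) = 0.26 SD. Adjusted for the entry value, multiply by √(1 − ρ²), where ρ is the entry–exit correlation. For an analysis of change, multiply by √(2(1 − ρ)). The documents do not give ρ:

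| Assumed ρ | Adjusted for entry | Change score |
|---|---|---|
| 0.5 | 0.22 | 0.26 |
| 0.7 | 0.18 | 0.20 |
| 0.9 | 0.11 | 0.12 |
| 0.95 | 0.08 | 0.08 |

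Even at ρ = 0.95, only r = 0.3 with prior use of 3–10 years gives an expected effect (0.085) above the half-width (0.081).

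**6. Does prior exposure help at month 12?** Given the entry value, the partial correlation of exposure with the exit value is r(1 − ρ)/√((1 − r²)(1 − ρ²)). At ρ = 0.9 this is 0.023 for r = 0.1 and 0.072 for r = 0.3. Squared, that is 0.05% to 0.5% of residual variance. The half-width moves from 0.1127 to no lower than 0.1124.

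**7. Why month-12 level and on-study dose stay out of the arm model.** Suppose the eye measure depends only on total dose, at 0.01 units per gram (assumed). The arm effect is then −0.01 × 83.5 = −0.835. With total dose held fixed it is zero, because arm acts only through dose. Month-12 level is also a consequence of arm and removes its effect in the same way.

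**8. Entry association.** With 256 patients, the correlation of an eye measure with duration of use has half-width 1.96/√253 = 0.12, or 0.12/√0.75 = 0.14 if age correlates 0.5 with duration (assumed). Selection pulls it down: if the worst 10% on the eye measure had already stopped HCQ (assumed, normal model), r = 0.30 would appear as about 0.26.

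**9. Binary retinopathy.** At assumed one-year frequencies of 1%, 2%, 5% and 10% in both arms, 256 patients yield about 3, 5, 13 and 26 cases. Power to detect a halving with 128 per arm is about 7%, 10%, 18% and 33%.

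**The case against.** The strongest reply is that nothing here is wrong. The objective asks for frequency by arm and a correlation with blood level, and randomisation answers the first without covariates. That stands. A reader might infer that ignoring prior exposure confounds the arm comparison. It does not, because prior use is balanced on average and the arms are themselves a contrast in cumulative dose.

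A second reply is that the generic t test could be run on change from entry, and that two examinations imply as much. At high ρ this would recover most of the precision, as step 5 shows. But no text says it will be done, and it would still not separate entry from new retinopathy or deal with withdrawals.

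A third reply is that no text claims a null one-year result would show the absence of toxicity. That is true; the risk lies in how readers take the result, and one sentence removes it.

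A further temptation is to think that adding pre-entry exposure would close the gap. The documents do not support that. Dose history is not on the data list, so time of use × 400 mg/day is duration on another scale. It misses earlier doses, which may have been lower in juvenile patients, and it misses non-adherence. It is entangled with age and disease duration and is open to selection. As a month-12 covariate it adds almost nothing once the entry value is in the model.

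**Conclusion.** The point holds as a modest improvement to a secondary safety objective; the primary flare analysis is untouched. 1B collects entry eye values and duration of HCQ use and states no eye analysis that uses either, although the plan names cumulative dose as the driver of retinopathy.

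The dose arithmetic rests on the documents, apart from the 10-year example. The precision gain depends on the assumed ρ, and the expected effects depend on the assumed spread of prior use and the assumed r. Under nearly all of these assumptions the one-year effect of cumulative dose is smaller than the trial can resolve, even after adjustment. Better analysis therefore does not make a null result informative about long-term toxicity, and the cautionary sentence is needed as well. At its lower bound (r = 0.1) the entry association could not be told apart from zero either.

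**What to change.** Main change, at no cost beyond SAP wording:

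- Compare the continuous SD-OCT and 10-2 field measures between arms at month 12, adjusted for the entry value.
- Report retinopathy present at entry separately from new cases, and count patients withdrawn for retinopathy as cases. Keep the binary comparison, labelled exploratory.
- Do not put month-12 blood level or on-study dose in the model that estimates the arm effect. Keep the planned blood-level correlation as a separate analysis. Pre-entry exposure is not needed as a month-12 covariate.

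Exploratory addition, at the cost of a little analysis time:

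- At entry, regress the continuous eye measures on recorded time of HCQ use, adjusted for age, with a sensitivity analysis adding disease duration.
- Label it a duration proxy, not cumulative dose. State that earlier doses (especially in juvenile lupus) and adherence are not captured, and that patients harmed by long use may already have stopped, which biases the association toward null.

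Add one sentence to the SAP: a null one-year result by arm or blood level, or a null entry association, is not evidence against cumulative-dose toxicity.

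No visits, patients or measurements are added, and the planned comparisons remain.

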Adherence will be assessed by the MASRI questionnaire applied by a pharmacist not directly involved in patient care (Koneru et al., 2007).

The following clinical, laboratory and treatment data will be evaluated in the groups (active disease and inactive disease): age, sex, race, weight, height, BMI, ideal weight; disease time, time of HCQ use, adherence to treatment; smoking; use and dose of prednisone, methotrexate, azathioprine, mycophenolate mofetil, cyclophosphamide, non-hormonal anti-inflammatory drugs; urinary protein/creatinine ratio; serum creatinine; blood concentrations of HCQ by HPLC; specific adverse events.

- Complete ophthalmologic assessment (at the entrance and at the end of the study), including campimetry and SD-OCT measurements, with segmentation of the outer layer of the retina (pigmentary epithelium).

- The production of interferon-alpha and TNF-alpha by plasmacytoid dendritic cells will be evaluated in vitro using mononuclear cell preparations isolated from peripheral blood from a random sample of the same number of consecutive patients with active and inactive SLE. The cells will be stimulated with the TLR-9 agonist, Oligodeoxynucleotide S CpG (ODN CpG-A)-2216 and with the TLR-7 agonist, imiquimod. The percentage of monocytes, B cells, dendritic cells and natural killers (NK) in the PBMC fraction will be determined by the phenotypic characterization of these cell subpopulations by flow cytometry using monoclonal fluorochrome-conjugated antibodies. Intracellular detection of IFN-alpha and TNF-alpha in plasmacytoid dendritic cells will also be performed by flow cytometry and specific monoclonal antibodies (Sacre et al., 2012).

- Establishment of a pharmacokinetic-pharmacodynamic model of hydroxychloroquine use with two groups of 5 patients: one with 5mg/kg/day daily and another 5mg/Kg/day 3 times a week. On inclusion both will be on hydroxychloroquine use for at least 6 months and should have the stable level of the drug (> 1000ng/mL).

Outcomes: assessment on days 0 and 120 days.

a) Worsens no SLEDAI -2K. Change in SLEDAI-2K evaluating activity criteria from 0-105 in 9 organs and 24 items (clinical and laboratorial). The increase represents clinical/laboratory worsening of the disease.

b) Cytokine measurement. Plasma levels of TNF- α and IFN-1 will be determined by Luminex MAP (EMD Millipore Corporation®). Plasma samples will be stored at -80oC until use.

TARGET POPULATION

Inclusion criteria:

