- Evaluate the clinical/laboratory response and adverse events in both groups.
- Verify a possible correlation of HCQ concentrations in blood and saliva with interferon-alpha and TNF production levels by plasmacytoid dendritic cells and disease activity parameters.
- Correlate blood and salivary levels of HCQ and its metabolites in Patients with SLE with adherence to this treatment.

NUMBER OF INDIVIDUALS

Total patients needed for the study = 96 (SLE).

STUDY DESIGN

Prospective randomized study controlled for a period of six months of patients with SLE who will start the use of HCQ.

Patients will be randomized randomly into two groups: traditional group - without increasing the daily dose (HCQ 400 mg/day); attack dose group - with increased daily dose (HCQ 800 mg/day for 6 months). Patients will be evaluated for the activity of the underlying disease in a "blind" way. HCQ concentrations will be assessed at the entrance and at the end of the study.

The groups will be compared for episodes of disease activity (clinical and laboratory parameters), inflammatory cytokines, and expression of TLR-7 and TLR-9 receptors.

Blood concentrations of HCQ and metabolites will be determined in both groups by HPLC (Munster et al., 2002).

The following indexes will be used to assess disease activity:

- SLE: SLEDAI-2K (Gladman et al., 2002) and active disease randomly defined as SLEDAI-2K \geq 6.

- Renal activity: BP, urine type I, protein and creatinine in an isolated urine sample, serum creatinine, C3, C4, anti-dsDNA, according to the ACR Guidelines (Hahn et al., 2012).

Adherence will be assessed by the MASRI questionnaire applied by a pharmacist not directly involved in patient care (Koneru et al., 2007).

The following clinical, laboratory and treatment data will be evaluated in the groups (traditional dose and attack dose): age, sex, race, weight, height, BMI, ideal weight; disease time, time of HCQ use, adherence to treatment; smoking; use and dose of prednisone, methotrexate, azathioprine, mycophenolate mofetil, cyclophosphamide, non-hormonal anti-inflammatory drugs; urinary protein/creatinine ratio; serum creatinine; HCQ blood concentrations by HPLC MS/MS; general- gastrointestinal and cutaneous adverse events.

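### The secondary correlations of HCQ level with adherence in 1B and 1C carry no adjustment for randomised dose, which differs 2.33-fold and 2-fold between the arms

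*Combined protocol and SAP*

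**What the plan says.** In subproject 1B the secondary objectives include "Correlate blood and salivary levels of HCQ and its metabolites in patients with SLE and JSLE with adherence to this treatment". In subproject 1C the matching objective is "Correlate blood and salivary levels of HCQ and its metabolites in Patients with SLE with adherence to this treatment".

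The dose is what each trial randomises. 1B compares a "no daily dose reduction group (HCQ 400 mg/day) and reduction group (HCQ 400 mg/day - 3X week"). 1C compares 400 mg/day with an arm "with increased daily dose (HCQ 800 mg/day for 6 months").

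Levels are sampled as follows. In 1B, "HCQ concentrations will be measured at the entrance, 6 months and 12 months after". In 1C, "HCQ concentrations will be assessed at the entrance and at the end of the study". At entry to 1B everyone is on the same dose, since the inclusion criterion is "use of HCQ at a dose of 400 mg/day for at least 3 years" (the 1B study design says five years, but at that same dose).

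For adherence, both trials state: "Adherence will be assessed by the MASRI questionnaire applied by a pharmacist not directly involved in patient care". No visit, scale, SD or expected arm difference for MASRI is given.

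The statistical paragraphs of 1B and 1C name the log-rank test, Fisher or chi-square tests, and t or Mann-Whitney tests. They name no correlation method, no stratification by arm and no dose-adjusted level.

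**The concern.** A blood level can stand for adherence only among patients prescribed the same amount of drug. In 1B and 1C the prescribed amount is split by design. If levels are proportional to dose, a fully adherent patient in the reduced arm of 1B has the same expected level as a standard-arm patient who takes 43% of the tablets (1200/2800). The level cannot then be read as adherence without knowing the arm.

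Two things follow if one correlation is run over all patients of a trial after randomisation. The spread in level caused by dose dilutes any true relation. And if reported adherence differs between the regimens, the pooled coefficient picks up that difference even when level and adherence are unrelated within each arm. The sign of the false correlation depends on which arm reports lower adherence. Use of levels to monitor adherence is a stated aim of the programme, so a diluted or confounded coefficient would be read as evidence on that aim.

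**Working it through.** **Figure in the plan.** The documents give no figure for this correlation. The 1C sample-size section does give a level distribution that can be checked: 870.3 ± 329.3 ng/mL at 400 mg/day, with about 34% above 1000. Under a normal distribution, (1000 − 870.3)/329.3 = 0.394, and the upper tail is 34.7%. This reproduces.

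**Inputs from the documents**
- Dose ratios: 2800/1200 = 2.33 (1B); 800/400 = 2.0 (1C).
- Level CV: 329.3/870.3 = 38% (1C sample size); 526/1079 = 49% (inactive SLE, 1A sample size).
- Half-life about 40 days. At 180 days, 1 − 2^(−180/40) = 96% of the shift to a new steady state is complete, so the arms have separated by month 6.
- Numbers after 10% loss: 128 × 0.9 ≈ 115 per arm (1B); 96/2 × 0.9 ≈ 43 per arm (1C, taking 96 as the total, as stated).

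**Assumptions, not in the documents.** Levels proportional to dose; adherence mean 80%, SD 15 points, capped at 100%; lognormal level error.

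**Share of level variance due to arm**, R² = (diff²/4) / (diff²/4 + mean within-arm variance). For 1B with 1079 ± 526 and constant CV, the reduced arm is 462 ± 225. Then diff²/4 = 617²/4 ≈ 95,000, the mean within-arm variance is (526² + 225²)/2 ≈ 163,700, and R² ≈ 0.37. Varying the mean, the SD, and constant SD against constant CV gives 25–49% in 1B and 30–64% in 1C.

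**Hand check on the product-moment scale.** A within-arm r is multiplied by √(1 − R²) = √0.63 ≈ 0.80. With no within-arm relation, the induced r is √R² × d/√(d² + 4), where d is the arm difference in adherence in SD units. For 5 points, d = 5/15 = 0.33 and r = 0.606 × 0.164 ≈ 0.10. The critical |r| is 0.13 with n = 230 and 0.21 with n = 86.

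**Simulation with Spearman correlation** (6,000 trials per cell; ranges run over CV 38–49%):

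| | 1B | 1C |
|---|---|---|
| True relation: within-arm r | 0.35–0.42 | 0.35–0.42 |
| Same data pooled: r | 0.26–0.28 | 0.28–0.31 |
| No relation, arms equal in adherence: p<0.05 | 5% | 5% |
| No relation, arms 2 points apart | 11–12% | 6–7% |
| No relation, arms 5 points apart | 39–48% | 14–19% |
| Same nulls, partial Spearman adjusted for arm | about 5% | about 5% |

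In the 5-point 1B case the induced r is about 0.11 to 0.13. It is positive if the reduced-dose arm reports lower adherence. In 1C, lower adherence in the 800 mg arm gives a negative r.

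**Power.** With a true relation and no arm difference, the pooled test has about 98% power in 1B. In 1C it has about 85% at CV 38% and 76% at CV 49%, against 98% and 91% within arm. For a weaker within-arm r of 0.30 on the product-moment scale, 1C falls from about 80% to 39–57%. With that same r in 1B and adherence 0.3 SD lower in the standard-dose arm, pooled power is 48% against 99% after adjustment.

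**1C under its own planning figure.** The plan expects 55% above 1000 ng/mL at 800 mg/day. At constant SD this implies a mean of 1000 + 0.126 × 329.3 ≈ 1041, a ratio of 1041/870.3 ≈ 1.2. Arm then explains about 6% of level variance, attenuation is negligible (0.42 to 0.41), and the false-positive rate at 5 points is about 6%.

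**The case against.** The strongest reply is that the documents are silent rather than wrong. A reader might infer that the plan pools raw levels across arms. It does not say so: neither objective mentions raw levels, pooling or a visit, and no correlation method is named. That stands. What remains is that the objectives are worded over the trial's patients and nothing in either plan would stop an analyst from following that wording.

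A reader might also infer that dose swamps adherence. It does not. Under dose proportionality, arm explains a quarter to a half of level variance in 1B and 30–64% in 1C, and the pooled 1B test still detects a true within-arm relation of 0.35–0.42 in about 98% of trials if adherence is equal between arms.

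Nor do the documents support the inference that any small MASRI difference creates a false finding. They give no expected difference. Randomisation rules out a systematic one at entry, although daily and three-times-weekly dosing could produce one later. At 2 points the 1B rate only about doubles, to 11–12%.

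Dose proportionality is itself an assumption, and 1C's planning figures contradict it: a doubled mean would put 87–99% of patients above 1000 ng/mL, not 55%.

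Finally, 1A studies level against questionnaire in patients on one dose range without a randomised split, so the programme's adherence aim does not rest on 1B and 1C alone. This too stands, and it limits the importance of the point.

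**Conclusion.** The point holds as a gap in the analysis of a secondary objective, and mainly for 1B. A correlation run as the objectives are worded, on post-randomisation samples, mixes assigned dose with adherence. With dose-proportional levels, an adherence SD of 15 points and a level CV of 38–49%, it lowers a within-arm r by roughly a quarter to a third in 1B (0.35 to 0.26; 0.42 to 0.28). It also leaves the test open to a false-positive rate of 39–48% if the arms differ by 5 points in adherence. With no arm difference there is no inflation.

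For 1C the effect is smaller and conditional. The clearer harm there is lost signal, and it nearly disappears if the arms separate only as far as 1C's own sample-size section expects.

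A reader might conclude that the 1B entry level should be discarded. That does not follow: it is taken while all patients are on 400 mg/day, before the doses diverge, and it is free of this confounding. The primary comparisons, flare in 1B and time to 1000 ng/mL in 1C, are untouched.

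**What to change.** Add one sentence to each statistical plan. For post-randomisation visits (months 6 and 12 in 1B, month 6 in 1C), compute the correlation of HCQ level with MASRI within each randomised arm and combine the two, as a stratified Spearman or a partial Spearman adjusted for arm. An alternative is to correlate MASRI with level divided by prescribed dose, but that relies on dose proportionality, so the arm-adjusted form is the safer main analysis. State the visit at which MASRI is taken and pair it with the level from the same visit. In 1B the entry sample may be kept and analysed without arm adjustment, reported separately from the later visits. In the simulations the arm-adjusted test held its false-positive rate at about 5% throughout and recovered the within-arm correlation. The change needs no new data, visits or patients.
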